3.10.2 Survival status for withdrawn consent and lost to follow up patients

At the time of primary analysis, the survival status of all patients in the full analysis set should be re-checked, this includes those patients who withdrew consent or are classified as "lost to follow up."

- Lost to Follow up – site personnel should check hospital records, the patients' current physician, and a publicly available death registry (if available) to obtain a current survival status in the 2 weeks following data cut-off. (The SURVIVE module will be updated.)
- In the event that the patient has actively withdrawn consent to the processing of their personal data, the survival status of the patient can be obtained by site personnel from publicly available death registries or resources (if available) where it is possible to do so under applicable local laws to obtain a current survival status in the 2 weeks following data cut-off. (The SURVIVE module will be updated.)

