- t. Eight PK samples per patient (4 samples for cediranib and 4 samples for olaparib) will be collected at steady state: 2 samples on Week 4 and 2 samples on Week 8 visit for cediranib and olaparib each. At the Week 4 visit, the first 2 samples should be taken 0.5 hours prior to the first dose of cediranib at the Week 4 visit; the second 2 samples should be taken 1 to 3 hours after the first dose of olaparib at the Week 4 visit. At the Week 8 visit, 2 samples should be taken 0.5 hours prior to the dose of cediranib administration; the second 2 samples should be taken 1 to 3 hours after the first dose of olaparib at the Week 8 visit.
- u. Assessments for survival should be made every 8 weeks (relative to first dose) following objective disease progression. Survival information may be obtained via telephone contact with the patient, patient's family or by contact with the patient's current physician. Subsequent anticancer therapies should also be recorded. Patients should be contacted or other data sources checked (see Section 3.10.2) in the 2 weeks following the data cut-off for the primary analysis to provide current complete survival data.

- v. Missed doses of study medications will be reported by patients using a handheld electronic device. These data will be reviewed by the Investigator at each patient visit and data entered in eCRF.
- Abbreviations: AE adverse event; ALT alanine transferase; AST aspartate transferase; *BRCA* breast cancer resistance protein; CA-125 cancer antigen-125; CT computed tomography; ctDNA circulating tumor DNA; ECG electrocardiogram; ECOG Eastern Cooperative Oncology Group; eCRF electronic case report form; EORTC European Organization for Research and Treatment of Cancer; FPV final protocol visit; FT4 free thyroxine; IP investigational product; LVEF left ventricular ejection fraction; MRI magnetic resonance imaging; N/A not available; PBMC peripheral blood mononuclear cells; PK pharmacokinetics; PRO-CTCAE Patient-Reported Outcomes version of the Common Terminology Criteria for Adverse Events; QLQ quality of life questionnaire; SAE serious adverse event; TSH thyroid stimulating hormone; UPC urine protein:creatinine ratio.

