Overall visit assessments will be determined for each assessment (scheduled or unscheduled) and will contribute to the derivation of PFS. Objective disease progression is defined as: at least a 20% increase in the sum of the diameters of the target lesions (compared with a previous minimum sum) and an absolute increase of >5 mm, an overall assessment of progression or a new lesion.

Overall survival (OS)

OS is defined as the time from the date of first dose until death due to any cause. Any patient not known to have died at the time of analysis will be censored based on the last recorded date on which the patient was known to be alive.

Note: Survival calls will be made in the 2 weeks following the date of the data cut-off for the primary analysis, and if patients are confirmed to be alive (or if the death date is post the relevant data cut-off date) these patients will be censored in the associated analyses at the date of the data cut off.

Time to discontinuation of IPs or death (TDT)

TDT is defined as the time from the date of first doses of IPs to the earlier of the date of discontinuation of both IPs, or death date. Both IPs should be discontinued at the same time but in rare circumstances discontinuation of one of the IPs before the other may be allowed (see Section 3.9). In such a case, TDT will reflect the time from the date of first dose to the earliest IP discontinuation date.

HRQoL Analyses:

The EORTC-QLQ-C30 and EORTC-QLQ-OV28 questionnaires will be used. Descriptive statistics of absolute scores and change from baseline of all subscales will be presented and plots will be generated as appropriate to interpret changes over time.

Proportions of patients who had improved, stayed the same or deteriorated for all subscales (symptom and functioning scales) will be presented. A 10 point change in score will be used as cut-off point. The quantity and impact of missing data will be evaluated. If warranted, some investigation of HRQoL data by whether patients are still taking study drug will be performed.

- Symptom Improvement Rate at 8 weeks
 - For dyspnea, pain and constipation from QLQ-C30 and abdominal/GI symptoms from QLQ-OV28, the symptom improvement rate at 8 weeks will be defined as the number (%) of patients showing a clinically meaningful improvement (a decrease from baseline score >10 ; Osoba et al 2005) in that symptom from baseline. The denominator will consist of a subset of the FAS population who have a baseline symptom score >10 .

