- For ICR assessments, the date of progression will be determined based on the **earliest** of the scan dates of the component that triggered the progression for the adjudicated reviewer selecting PD or of the reviewer who read baseline first if there is no adjudication for ICR data.

- For Investigator assessments, the date of progression will be determined based on the **earliest** of the dates of the component that triggered the progression.
- For both ICR and investigator assessments, when censoring a patient for PFS the patient will be censored at the **latest** of the dates contributing to a particular overall visit assessment.

Note: for TLs only the latest scan date is recorded out of all scans performed at that assessment for the TLs and similarly for NTLs only the latest scan date is recorded out of all scans performed at that assessment for the NTLs.

Overall visit assessments will be determined for each assessment (scheduled or unscheduled) and will contribute to the derivation of PFS. Objective disease progression is defined as: at least a 20% increase in the sum of the diameters of the target lesions (compared with a previous minimum sum) and an absolute increase of >5 mm, an overall assessment of progression or a new lesion.

Overall survival (OS)

Overall survival is defined as the time from the date of first dose until death due to any cause regardless of whether the patient withdraws from treatment or receives another anti-cancer therapy (i.e. date of death or censoring – date of first dose + 1). Any patient not known to have died at the time of analysis will be censored based on the last recorded date on which the patient was known to be alive.

Survival calls will be made in the 2 weeks following the date of the data cut-off for the primary analysis, and if patients are confirmed to be alive (or if the death date is post the relevant data cut-off date) these patients will be censored in the associated analyses at the date of the data cut off. Data will be recorded on the SURVIVE module of the eCRF and this dataset will be used as priority for analysis.

For the OS analysis for the primary analysis at the 8 month DCO the Date last known alive on survival status CRF (SURVIVE: SUR_DAT) will be used.

If this date is missing the last date for each individual patient is defined as the latest among the following dates recorded on the case report forms (CRFs):

- AE start and stop dates (AE: AESTDAT, AEENDAT)

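### The OS derivation uses the SURVIVE date whenever one exists, so a few patients with later proof of life on another form may be censored too early

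*SAP*

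**What the plan says.** **General rule.** SAP 3.2.2 says a patient not known to have died "will be censored based on the last recorded date on which the patient was known to be alive". Protocol 8.4.2 has the same rule: "Any patient not known to have died at the time of analysis will be censored based on the last recorded date" on which she was known to be alive. Neither statement ranks one form above another.

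**Derivation.** SAP 3.2.2 then gives programming instructions. Of the SURVIVE data it says "this dataset will be used as priority for analysis". For OS at the 8-month cut-off, "the Date last known alive on survival status CRF (SURVIVE: SUR_DAT) will be used". The other forms come in only conditionally: "If this date is missing the last date for each individual patient is defined as the latest among the following dates recorded". The list that follows covers adverse event, hospitalisation, dosing, laboratory, vital sign, scan, subsequent anticancer therapy, post-treatment radiotherapy, end-of-study and visit dates. No step takes the later of SUR_DAT and these dates, and the list states no cap at the data cut-off.

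**Safeguards.** Survival calls are made in the 2 weeks after the cut-off, and "if patients are confirmed to be alive (or if the death date is post the relevant data cut-off date) these patients will be censored" at the cut-off date. Protocol 3.10.2 adds that "the survival status of all patients in the full analysis set should be re-checked", including patients who withdrew or were lost, with the SURVIVE module updated.

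**The concern.** The rule and its derivation can give different dates for the same patient. When SUR_DAT is older than another record showing the patient alive, the derivation discards the later record. The SAP's amendment history says the last-date calculation in this section was clarified in the September 2019 amendment, so programmers can be expected to follow it literally.

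The result can also be perverse. A patient with no SURVIVE date gets the latest date across all forms, while a patient with an old one does not, so having more survival data can produce the worse censoring date.

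At stake is a small downward shift in the Kaplan-Meier OS estimate, because follow-up is removed only from patients who have not died.

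**Working it through.** **Step 1. The two rules applied to one patient (illustrative dates).** SUR_DAT is at month 8, a laboratory or subsequent-therapy record is at month 9.5, and there is no contact after the cut-off.

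| Situation | General rule | Derivation |
|---|---|---|
| As described | month 9.5 | month 8 |
| Same patient, SUR_DAT missing | month 9.5 | month 9.5 |
| Same patient, confirmed alive after cut-off | cut-off date | cut-off date |

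The rules differ only in the first row. That needs a living patient not confirmed alive after the cut-off, a non-missing SUR_DAT, and a later valid date on another form.

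**Step 2. Direction.** At a death with n patients at risk, Kaplan-Meier multiplies the estimate by 1 − 1/n. Removing one living patient early makes this 1 − 1/(n − 1), which is smaller. With n = 20 for illustration, 0.9500 becomes 0.9474. The estimate can only stay the same or fall.

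**Step 3. How many patients are censored.** Protocol 8.2 and SAP 1.3 give about 60 patients, median OS 12 months, median PFS 6 months, analysis 8 months after the last first dose, and 57% OS and 80% PFS events. With exponential survival and uniform accrual over A months, the event fraction is

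1 − exp(−λF) × (1 − exp(−λA)) / (λA), where λ = ln 2 / median and F = 8.

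The revised accrual length is not stated. A = 14 gives:

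- OS: λ = 0.0578, and 1 − 0.630 × 0.555 / 0.809 = 56.8% (stated 57%).
- PFS: λ = 0.1155, and 1 − 0.397 × 0.802 / 1.617 = 80.3% (stated 80%).

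A = 12 gives 54.6% and 78.5%; A = 24 gives 65.9% and 86.6%. So A = 14 is a calibration to the stated figures, not a figure from the plan. At 57%, 0.57 × 60 ≈ 34 patients have died and about 26 are censored.

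**Step 4. Effect on OS.** The trial was simulated with N = 60, median OS 12 months, uniform accrual over 14 months, cut-off at month 22 and 2,500 runs per scenario. All deaths up to the cut-off were taken as known. Three inputs are assumptions:

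- 5%, 10% or 20% of living patients are not reached, and every one of them has an older SUR_DAT and a later date elsewhere;
- her latest date on any form falls uniformly between 50% and 100% of her potential follow-up;
- SUR_DAT is 4, 8 or 16 weeks older than that date. Eight weeks is the protocol's contact interval: "Assessments for survival should be made every 8 weeks (relative to first dose) following objective disease progression".

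| Not reached | Lag (weeks) | Mean patients affected | Change in median OS (months) | 12-month OS, latest date | 12-month OS, SUR_DAT first | Drop (points) | Person-time lost |
|---|---|---|---|---|---|---|---|
| 5% | 4 | 1.3 | −0.02 | 49.81% | 49.73% | 0.08 | 0.2% |
| 5% | 8 | 1.3 | −0.05 | 49.70% | 49.55% | 0.15 | 0.4% |
| 5% | 16 | 1.3 | −0.08 | 49.76% | 49.47% | 0.29 | 0.8% |
| 10% | 4 | 2.6 | −0.05 | 49.56% | 49.41% | 0.15 | 0.4% |
| 10% | 8 | 2.6 | −0.10 | 49.70% | 49.39% | 0.31 | 0.8% |
| 10% | 16 | 2.6 | −0.20 | 49.66% | 49.02% | 0.64 | 1.7% |
| 20% | 4 | 5.1 | −0.08 | 49.18% | 48.87% | 0.31 | 0.8% |
| 20% | 8 | 5.2 | −0.19 | 49.13% | 48.46% | 0.67 | 1.7% |
| 20% | 16 | 5.2 | −0.41 | 49.06% | 47.73% | 1.33 | 3.4% |

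The other planned landmarks (3, 6 and 18 months) were not computed.

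**The case against.** **The field already holds the right date.** SUR_DAT is labelled as the date last known alive, and sites complete survival status from notes, hospital records, the patient's physician and death registries. If every site does this fully, SUR_DAT is the latest date and the rules agree. This is a fair reading of intent, but the SAP has no step to catch an entry that was not brought up to date.

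**The re-check covers the patients in question.** It applies to the whole full analysis set, including lost and withdrawn patients, and this narrows the problem greatly. It does not close it. Where consent to data processing has been withdrawn, protocol 3.10.2 points only to public registries or resources, if available and lawful. A death registry can show a death, but the absence of an entry gives no last-alive date.

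**Later dates elsewhere will be uncommon.** After treatment stops, routine laboratory tests end at the day-30 visit, scans follow the same 8-weekly schedule as survival contacts, and subsequent therapy is recorded during survival follow-up. This stands as a reason to expect few cases. Scans before progression, therapy dates and adverse events followed to resolution still leave room for some.

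**Stronger readings.** A reader might infer that OS is censored too early across the trial, or that known survival time is being lost in a group whose censoring is informative. The documents support neither. They give no count of affected patients, and nothing in them shows that censoring is related to prognosis. Moving a censoring date by some weeks also leaves any such dependence much as it was. Nor is 8 weeks a strict limit on the loss, since a contact can be missed.

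**Conclusion.** The point holds as a minor inconsistency. As written, the derivation departs from the SAP's and protocol's own censoring rule for living patients who are not confirmed alive after the cut-off, have an older SUR_DAT, and have later proof of life on another form. For them it censors too early, and the bias is towards shorter OS.

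The number of such patients is unknown. The middle scenario (10% not reached, 8-week lag) costs about 0.3 points of 12-month OS and 0.10 months of median OS. These sizes rest on the assumed non-contact rates and lags, exponential survival and 14 months' accrual. Counting every unreached patient as affected makes each scenario pessimistic for its non-contact rate.

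OS is summarised descriptively in a single-arm study, with no comparator or test. The conclusion on ORR does not depend on this derivation.

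**What to change.** In SAP 3.2.2, replace the SURVIVE-first fallback with a single rule: for patients not known to have died, the OS censoring date is the latest of SUR_DAT and those listed CRF dates that show the patient was alive, and never later than the data cut-off. Visit, laboratory, vital sign, scan, dosing, hospitalisation and subsequent-therapy dates are examples.

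Exclude the end-of-study date (DS: DSSTDAT) where it is administrative, such as the day loss to follow-up was declared. A reader might take the change to be free of risk because it simply uses the maximum of the whole list. That does not follow: a date that does not prove life could override a site-verified one and overstate survival in the same lost or withdrawn patients.

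The cost is one SAP sentence, one line of code and a check before database lock that the qualifying dates are true patient contacts. Where SUR_DAT is already the latest qualifying date, nothing changes.

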3.10.1 Withdrawal of the informed consent

Patients are free to withdraw from the study at any time (IPs and assessments), without prejudice to further treatment.

A patient who withdraws consent will always be asked about the reason(s) and the presence of any AEs. The Investigator will follow up AEs outside of the clinical study.

If a patient withdraws from participation in the study, then her enrollment code cannot be reused. Withdrawn patients will not be replaced.

If the patient is lost to follow-up, the Investigator should make every reasonable effort to contact the patient or a responsible relative. Patients will be considered lost to follow-up only if no contact has been established at any time up to data cut-off for the primary analysis, such that there is insufficient information to determine the patient's status at that time. Patients who refuse to continue participation in the study, including telephone contact, should be documented as "withdrawal of consent" rather than "lost to follow-up." Investigators should document attempts to re-establish contact with missing patients throughout the study period. If contact with a missing patient is re-established, the patient should not be considered lost to follow-up and any evaluations should resume according to the protocol.

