- Admission and discharge dates of hospitalization (SERAE: AESHODAT, AESDIDAT)
- Study treatment date (EX & EX1: EXSTDAT)
- End of treatment date (EX & EX1: EXENDAT)

28(56)

89 of 118

- Laboratory collection dates (LB & LB1-6: LBDAT)
- Date of vital signs (VS & VS1: VSDAT)
- Disease scan dates on RECIST CRF (1,3RECIST1: R1ASMDAT)
- Start and stop dates of alternative anticancer treatment (CAPRX1: CXSDAT, CXEDAT)
- Start and stop dates of post-IP radiotherapy (CAPRXR1: CXRDSDAT, CXRDEDAT)
- End of study date (DS: DSSTDAT)
- Visit date (VISIT: VIS_DAT)

The status of ongoing, withdrawn (from the study) and “lost to follow-up” patients at the time of the final OS analysis should be obtained by the site personnel by checking the patient’s notes, hospital records, contacting the patient’s general practitioner and checking publicly-available death registries. In the event that the patient has actively withdrawn consent to the processing of their personal data, the vital status of the patient can be obtained by site personnel from publicly-available resources where it is possible to do so under applicable local laws.

Best objective response (BoR)

Best objective response (BoR) is calculated based on the overall visit responses from each RECIST assessment, described in section 3.1.3. It is the best response a patient has had following start of treatment, but prior to starting any subsequent cancer therapy and up to and including RECIST progression or the last evaluable assessment in the absence of RECIST progression. Categorisation of BoR will be based on RECIST using the following response categories: CR, PR, SD, PD and NE.

CR or PR must be confirmed. For determination of a best response of SD, the earliest of the dates contributing towards a particular overall visit assessment will be used. SD should be recorded at least 8 weeks minus 1 week, i.e. at least 49 days (to allow for an early assessment within the assessment window), after start of treatment. For CR/PR, the initial overall visit assessment which showed a response will use the latest of the dates contributing towards a particular overall visit assessment.

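### When the survival-form date is missing, the OS fallback can censor a lost patient at an end-of-study date that need not show she was alive

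*SAP*

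**What the plan says.** SAP 3.2.2 (Overall survival) sets the principle that a patient not known to have died is "censored based on the last recorded date on which the patient was known to be alive". For the analysis at the 8-month cut-off, "the Date last known alive on survival status CRF (SURVIVE: SUR_DAT) will be used", and of the SURVIVE data the SAP says that "this dataset will be used as priority for analysis".

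The fallback follows: "If this date is missing the last date for each individual patient is defined as the latest among the following dates recorded". The list covers adverse event dates, hospital admission and discharge, dosing, laboratory samples, vital signs, scans, later anticancer treatment and radiotherapy, visits, and one disposition item, "End of study date (DS: DSSTDAT". No condition is placed on the disposition reason. No cap at the data cut-off is written for these dates.

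Protocol 3.10.1 restricts when the label of lost may be given: "lost to follow-up only if no contact has been established at any time up to data cut-off".

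**The concern.** The other items on the list date something that happened to the patient or was done with her. The end-of-study date records a change of status and does not by itself imply contact. Because the rule takes the latest date, this item overrides every real contact whenever it is later.

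Under Protocol 3.10.1 the label of lost to follow-up cannot be settled until about the cut-off, which may be months after the last contact. If a site enters the date on which it reached that conclusion, the patient stays in the Kaplan-Meier risk set over a period when her death could not have been seen. That pushes the OS curve, its median and the 6-, 12- and 18-month proportions upward. In a single-arm trial OS can be read only against outside figures, such as the roughly 12 months given in Protocol 1.1.1, and the cut-off analysis is the final one.

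**Working it through.** **1. The texts side by side.** The principle needs evidence of life on the censoring date. The fallback needs only that a date exists and is the latest. The two agree if the end-of-study date is a contact date and conflict if it is not. Neither document says which it is for a lost patient.

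**2. The cap.** SAP 3.2.2 censors at the cut-off those patients whom the survival calls confirm alive, or who die after it. It says nothing similar for fallback dates. SAP 3.3.1, by contrast, writes the cut-off explicitly into exposure and safety follow-up as one term of a minimum.

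**3. Inputs for sizing.** From SAP 1.3: about 60 patients, cut-off 8 months after the last first dose, assumed median PFS 6 months and OS 12 months, and 80% PFS and 57% OS events expected. The revised accrual period is not stated. Nor is the number of patients who would reach the fallback.

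**4. Reproducing the plan's event figures.** With exponential survival of median M and uniform accrual over A months, the expected event share is

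1 − [M / (A ln 2)] × [exp(−8 ln 2 / M) − exp(−(A + 8) ln 2 / M)].

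With A = 14:
- OS (M = 12): 1 − (0.6300 − 0.2806) / 0.8087 = 56.8%.
- PFS (M = 6): 1 − (0.3968 − 0.0787) / 1.6173 = 80.3%.

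A linearly rising accrual over 22 months gives 57.0% and 80.1%. The plan's pair is thus self-consistent once an accrual period is assumed, and no stated figure is shown to be wrong. I used both patterns below.

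**5. Size of the effect, if it occurs.** The Kaplan-Meier estimate is the product of (1 − d/n) over death times. A lost patient kept in n but unable to add to d lowers every d/n in the gap, so the error can only run upward. I simulated 4000 trials of 60 patients with true median OS 12 months. In each, a fixed number of living patients were lost independently of survival and had no SURVIVE date. They were censored either at last contact or at the cut-off.

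| When lost (assumed) | Affected | Median OS, censored at last contact | Median OS, censored at cut-off | 12-month OS, censored at cut-off |
|---|---|---|---|---|
| Any time in follow-up | 1 | 11.9–12.0 | 12.1–12.2 | 50.5% |
| Any time in follow-up | 3 | 11.9–12.0 | 12.4–12.5 | 51.4% |
| Any time in follow-up | 6 | 11.9–12.0 | 12.9–13.1 | 52.6–52.8% |
| Months 1–4 | 3 | about 12.0 | 12.7–12.8 | 52% |
| Months 1–4 | 6 | about 12.0 | 13.6–13.8 | 54% |

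Censoring at last contact gives a 12-month OS of about 50% throughout. When loss can occur at any time, each affected patient adds about 8.4 unobserved months, and about 36% of such patients would in truth have died in the gap.

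The shift in the median is therefore about 0.5 to 0.8 month for 3 of 60 and about 1.0 to 1.7 months for 6 of 60. A uniform 20-month accrual gives nearly the same shifts, although it does not match the plan's event figures (about 63% OS and 84% PFS events).

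**The case against.** A reader might infer that the end-of-study date is an administrative date for lost patients, so that OS in this trial is overstated. The documents do not support that. Protocol 3.10.1 says when a patient may be classified as lost, not which date goes on the disposition form. That form could hold the last contact, and Protocol section 5 refers to completion guidelines that are not part of these documents. For a patient who withdraws consent, the date may well be a real contact.

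The fallback also applies only when the SURVIVE date is missing, and the plan works to prevent that. Protocol 5.1.4 asks for survival contact every 8 weeks after progression or discontinuation. Protocol 3.10.2 requires a re-check of every treated patient, including lost and withdrawn ones, in the 2 weeks after cut-off, with the SURVIVE form updated. SAP 3.2.2 repeats the re-check directly below the list. A patient with any dated SURVIVE record never reaches the fallback. It would likewise go too far to say that those without a SURVIVE date are mainly patients lost before their first survival contact. The schedule makes that possible, since these contacts start only after progression or discontinuation, but nothing shows it.

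Finally, OS is descriptive. With 57% of 60, about 34 deaths, an approximate 95% interval for a 12-month median under an exponential model is 12 × exp(±1.96/√34), or 8.6 to 16.8 months. A half-month shift lies well inside that.

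All of this limits how often the problem occurs and how much it matters. It does not defend the rule. The re-check relies on records and registries that may be unavailable, and a check that fails leaves the patient's status unknown, which is where a non-contact date does harm. Sampling width also does not offset an error that runs in one direction.

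**Conclusion.** The point holds as a conditional one. The fallback admits a date not tied to proof of life, without regard to disposition reason and without a cap, so it can break the SAP's own censoring definition. Two things must both be true for any effect: the SURVIVE date is missing, and the end-of-study date is later than the last real contact. If either fails, the effect is zero, and the plan's safeguards may leave few or no patients exposed.

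The shifts given above rest on an assumed number of affected patients, exponential survival, loss independent of survival, and an end-of-study date equal to the cut-off. They show what could happen and are not a forecast. The primary response rate, the sample size and the futility rule are unaffected. The change is still worth making before database lock, because any error favours the treatment and the correction is nearly free.

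**What to change.** In the OS fallback of SAP 3.2.2:

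- Use the end-of-study date only where the disposition record documents contact with the patient on that date, for example consent withdrawn in person. Otherwise use the latest dated contact or assessment already on the list.
- Cap all fallback dates at the data cut-off.
- Report how many patients were censored by the fallback.

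The cost is a sentence or two of SAP text, one condition in the derivation and one count in the OS table. If the end-of-study date already holds the last contact, little is lost, because the other dated contacts stay on the list. The downside is that reported OS may be slightly less favourable.
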